#### 3.1.1 Dose-Finding Phase

The dose-finding phase will assess the safety of venetoclax when added to obinutuzumab and magrolimab. Up to 6 FL patients in Arm 1 will be treated and undergo DLT assessment during the first 4 weeks (Cycle 1) of triplet combination therapy with magrolimab, obinutuzumab and venetoclax. Venetoclax will be administered at DL1 without a safety ramp-up ([Figure 3](#)). If  $\geq$

patients experience DLT at DL1, up to 6 additional patients will be enrolled (Cohort 1, Arm 1) and treated at DL(-1) of venetoclax. Dose-finding will follow the rules mentioned in **Table 8**.

Up to 6 MZL, MCL or CLL patients treated in Arm 2 will undergo DLT assessment during the first 5 weeks of triplet combination therapy (Cycle 1). Venetoclax will be administered with a safety ramp-up to target dose (dose level 1) (**Table 10, Figure 4**). If  $\geq 2$  patients experience a DLT at DL1, up to 6 additional patients will be enrolled (Cohort 2, Arm 2) and treated at DL (-1) of venetoclax (**Figure 3**). Dose-finding will follow the rules mentioned in **Table 8**.

No more than 2 patients can be in a DLT assessment period at any given time. If a DLT has occurred, only 1 patient can be in the respective DLT assessment period at a given time. Patients who withdraw before completing DLT assessment for reasons other than a DLT, will not be evaluable for assessment of DLT for dose review decisions, and will be replaced.

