**Figure 3: Arm 1: FL Dose-finding**

**Figure 4: Arm 2: MZL, MCL and CLL Dose-finding**

**Figure 5: Arms 3 and 4 – Dose Expansion**

### 3.1.4 Dose-Limiting Toxicity

Dose limiting toxicities (DLTs) will be assessed during the venetoclax dose-finding for Arms 1 and 2 as follows:

- the first 4 weeks of triplet combination therapy for patients enrolled in Arm 1, Cohort 1 (C1D1 to C1D28)

- the first 5 weeks after starting venetoclax in Arm 2, Cohort 2 (C1D1 to C1D35).

Dose reductions of magrolimab and obinutuzumab are not permitted during DLT assessment period.

A DLT for this study is defined as any grade 3 or higher adverse event that is clinically relevant and deemed probably or definitely related to any of the study drugs or to the combination therapy, in the opinion of the Principal Investigator and occurs during the venetoclax dose-finding period with the exception of following:

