#### 3.1.4.1 Non-hematologic AEs

- Grade 3 nausea, vomiting, or diarrhea that persist  $\leq$  7 days with supportive care
- Grade 3 fatigue with improvement to  $\leq$  grade 2 within 7 days
- Grade 3 infection that improves to  $\leq$  grade 2 after initiation of antimicrobials
- Grade 3 electrolyte disturbances that improve to  $\leq$  grade 2 within 72 hours with appropriate medical management and are not associated with other clinically significant consequences.
- Grade 3 magrolimab- or obinutuzumab-infusion reactions that resolve to  $\leq$  grade 1 within 24 hours. **NOTE:** In a patient, if it is not clear if the AE is an infusion-related reaction (IRR), the patient may be replaced.
- Other grade 3 laboratory abnormality that is asymptomatic and deemed by the investigator to be not clinically significant

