### **8.1.5 Relationship to Study Product**

All AEs will have their relationship to study product assessed using the terms: related or not related.

- Related – There is a reasonable possibility that the study product caused the adverse event. Reasonable possibility means that there is evidence to suggest a causal relationship between the study product and the adverse event.
- Not Related – There is not a reasonable possibility that the administration of the study product caused the event.

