## 8.2 ASSESSMENT OF SAFETY EVENTS

AE information collected will include event description, date of onset, assessment of severity and relationship to study product and alternate etiology (if not related to study product), date of resolution of the event, seriousness and outcome. The assessment of severity and relationship to the study product will be done only by those with the training and authority to make a diagnosis and listed on the Form FDA 1572 as the site principal investigator or sub-investigator. AEs occurring during the collection and reporting period will be documented appropriately regardless of relationship. AEs will be followed through resolution.

SAEs will be:

- Assessed for severity and relationship to study product and alternate etiology (if not related to study product) by a licensed study physician listed on the Form FDA 1572 as the site principal investigator or sub-investigator.
- Recorded on the appropriate SAE report form, the medical record and captured in the clinical database.
- Followed through resolution by a licensed study physician listed on the Form FDA 1572 as the site principal investigator or sub-investigator.

For timeframe of recording adverse events, please refer to section [6.1](#). All serious adverse events recorded from the time of first investigational product administration must be reported to the sponsor with the exception of any listed in section [8.4](#).

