Based on these estimates, up to 24 patients may be required for venetoclax dose-finding. These, in addition to 42 total treated patients required to complete the dose expansion phase brings the total number of patients required to complete the study to 66. To allow for a small number of inevaluable patients and screen failures, the accrual ceiling will be set at 76 patients. It is expected that 3 to 4 years may be required to complete accrual, including dose-finding and expansion cohorts. Patients enrolled in dose-finding cohorts who are treated at the same dose-level as the expansion cohorts may be analyzed together with the dose-expansion cohorts at the end of the study (Cohort 1 with Cohort 3, and Cohort 2 with Cohorts 4, 5 and 6, respectively).

As mentioned earlier in Section [1.2.6.2.1.2](#), recent reports indicate that MZL patients may be at a higher risk of infection-related AEs with fatal outcome when obinutuzumab was used in combination with chemotherapy. As an early stopping rule, if  $\geq 2$  subjects have infection-related SAEs or any subject experiences a fatal infection-related AEs from the first 6 subjects on study, we will hold further enrollment, and a comprehensive safety analysis will be performed.

In addition, an early stopping rule will be implemented for all histologies, if a substantial number of patients have to discontinue therapy due to unacceptable toxicity. If at any point after the first 20 patients are enrolled, 25% or more patients have been unable to complete therapy due to unacceptable toxicity or if at any point 2 or more deaths or grade 4 hemolytic anemia events occur that are probably or definitely related to study therapy, then study enrollment for all histologies will be suspended for a formal assessment of the overall safety profile of the study design. This early stopping rule is applicable throughout the duration of the study.

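### The infusion-reaction NOTE in Section 3.1.4.1 allows replacement after a possible DLT has been seen, which can move the 2-of-6 dose decision either way; separately, the probable/definite causality judgement is not specified as recorded data

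*Combined protocol and SAP*

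**What the plan says.** **DLT count.** Subject to listed exceptions and to the Principal Investigator's judgement, Section 3.1.4 counts the following: "any grade 3 or higher adverse event that is clinically relevant and deemed probably or definitely related to any of the study drugs". Events attributed to the drugs acting together qualify too. One exception in Section 3.1.4.1 covers grade 3 magrolimab or obinutuzumab infusion reactions that settle to grade 1 or lower within 24 hours. Its NOTE adds: "if it is not clear if the AE is an infusion-related reaction (IRR), the patient may be replaced". The NOTE gives no criteria for unclear, no deadline and no second assessor.

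The general replacement rule in Section 3.1.1 is narrower: "Patients who withdraw before completing DLT assessment for reasons other than a DLT, will not be evaluable for assessment of DLT", and they are replaced.

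Under Table 8, fewer than 2 DLTs in 6 sends the dose to expansion, and 2 or more at DL1 leads to six patients at DL(-1). Section 10.4.2 makes the type, number and frequency of DLTs the primary analysis. Section 10.3.1 keeps everyone who received a dose in the toxicity population.

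**Causality scale.** Section 10.2 sets one of its stopping triggers as follows: "if at any point 2 or more deaths or grade 4 hemolytic anemia events occur that are probably or definitely related to study therapy". It names no assessor for that grade of causality. Meeting the trigger has this effect: "study enrollment for all histologies will be suspended for a formal assessment of the overall safety profile of the study design". Section 8.1.5 states: "All AEs will have their relationship to study product assessed using the terms: related or not related". Related there means: "There is a reasonable possibility that the study product caused the adverse event". Section 8.2 lists what is collected: "AE information collected will include event description, date of onset, assessment of severity and relationship to study product and alternate etiology". No probability grade is listed, and nothing maps one scale to the other.

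**The concern.** A dose-finding count is sound only if the rule for who belongs in it does not depend on the outcome being counted. Replacing a patient who withdraws for reasons other than a DLT respects that. Replacing a patient because a grade 3 event has occurred and is hard to classify does not: the decision is taken with the event in view.

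Unclear cases are foreseeable from the protocol itself. Section 3.3.5 says infusion reactions may look like IgE-mediated allergy, and Section 3.4.3.1 says hypersensitivity is hard to tell from them. In dose-finding (Table 11), obinutuzumab and venetoclax both start on Day 1, and both antibodies are given on Day 2. Section 3.3.4 sets a 24-hour assessment window for magrolimab reactions; Section 3.3.5 sets none for obinutuzumab.

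At stake is the venetoclax dose carried into expansion: up to 18 patients from Cohort 1's decision and up to 24 (6 + 12 + 6) from Cohort 2's, 42 in all.

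The causality mismatch matters less. It means that someone reading the specified adverse event data could not confirm whether the Section 10.2 trigger had been met, or why a related grade 3 event was not called a DLT.

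**Working it through.** **What the plan computes.** Section 10.2 gives only patient numbers. 6 + 6 + 6 + 6 = 24 for dose-finding and 18 + 6 + 12 + 6 = 42 for expansion give 66, which reproduces and is not disputed. The plan states no operating characteristics for the 2-of-6 rule and no rate of unclear events, so the rates below are assumptions.

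**One replacement.** Suppose the replacement patient has a 20% chance of a counted DLT.
- The six include 2 DLTs, one of them unclear. Replacing that patient leaves 1 of 5, and the sixth place brings the count back to 2 with probability 0.20. De-escalation is lost with probability 0.80.
- The six include 1 DLT and one unclear event that was really an exempt reaction. Replacing that patient turns 1 of 6 into 2 of 6 with probability 0.20. De-escalation is gained.

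**Over the cohort.** Let p be the true DLT rate and u the proportion of patients with an unclear event, all of whom are replaced. The chance of de-escalating is P(X ≥ 2) = 1 − (1 − q)^6 − 6q(1 − q)^5, where q is the DLT rate among counted patients:
- no replacement: q = p;
- replaced events were DLTs: q = (p − u)/(1 − u);
- replaced events were exempt reactions in patients without another DLT: q = p/(1 − u).

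| p | u | No replacement | Replaced events were DLTs | Replaced events were exempt |
|---|---|---|---|---|
| 0.20 | 0.05 | 0.345 | q = 0.15/0.95: 0.242 | q = 0.20/0.95: 0.370 |
| 0.30 | 0.10 | 0.580 | q = 0.20/0.90: 0.399 | q = 0.30/0.90: 0.649 |

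**Cost of counting ambiguous events.** If 5 points of exempt reactions are wrongly counted on a 20% true rate, q = 0.25 and P(X ≥ 2) = 0.466, against 0.345.

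**Section 10.2 threshold.** Suppose 1% of patients have a probably or definitely related qualifying event and a further 1% have one that is only possibly related. Lowering the trigger to related doubles the counted rate from 1% to 2%. The chance of two or more events rises from 0.10 to 0.29 in 54 patients (12 + 42, no de-escalation) and from 0.14 to 0.38 in 66. That is a change of threshold, not a clarification.

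**The case against.** **On the NOTE.** It is narrow, sitting under one exception for grade 3 events. The dose being sought is venetoclax's, so there is a rationale for not letting an antibody infusion reaction decide it. The 24-hour exemption already does that for recognised, short-lived reactions, however. The NOTE reaches the cases where the cause is not known, and the DLT definition covers toxicity from any study drug. The magrolimab window in Section 3.3.4 reduces the number of unclear cases but does not remove the discretion.

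A reader might infer that the NOTE favours the higher dose. The documents do not support that: removing an exempt reaction pushes the other way, and nothing shows which kind would predominate. Nor do the events vanish, because Section 10.3.1 keeps the patient in toxicity reporting. The grade 3–4 infusion-reaction rates quoted in the background do not size the problem either: they count all such reactions, including grade 4, not the unclear ones.

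**On causality.** A reader might infer that the Section 10.2 rule cannot be run, or that two related deaths could pass unexamined. Neither follows. Section 8.2 has every SAE assessed by a licensed study physician listed on Form FDA 1572, who can make a probable/definite judgement, and the case report form, which might hold such a field, is not in the documents. Other safeguards include the 25% discontinuation limb of Section 10.2, 24-hour SAE reporting (Section 8.3), committee review (Section 7.4.2), the conference on grade 3 or 4 hemolytic anemia (Section 7.4.1) and the general power to suspend (Section 13.1). None is an automatic two-death trigger, but together they reduce this part to a question of traceability. A higher bar than related may also be intended.

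**Conclusion.** The main point stands: as written, the NOTE lets a patient leave the six-patient DLT count because of an event already seen, against the principle of Section 3.1.1, and this can change the expansion dose and the DLT frequency reported as the primary result. The direction is not determined. In the two illustrations the chance of de-escalating moves from 0.35 to 0.24 or 0.37, and from 0.58 to 0.40 or 0.65. These figures rest on assumed DLT rates, assumed shares of unclear events and replacement of every unclear case; the documents supply none of these. Correcting it is a cheap improvement to a stated rule.

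The causality mismatch is real but minor. The probable/definite threshold can be applied by physician judgement; what is missing is a specified record of that judgement. Moving the Section 10.2 trigger down to related would be a sponsor's choice about how often to pause, not the correction of an error.

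**What to change.** **Section 3.1.4.1.** Replace the NOTE with: *A patient with a grade 3 event of unclear IRR status remains evaluable and is not replaced. An event that otherwise meets the DLT definition counts as a DLT unless the Principal Investigator documents it as an infusion reaction that resolved to grade 1 or lower within 24 hours, or it meets another listed exception.* Requiring a documented infusion reaction matters: exempting any unclear event that clears within 24 hours would let a brief DLT of another kind escape.

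The cost is amendment wording, plus some ambiguous reactions counted as DLTs. In the example above, that raises the chance of de-escalating from 0.35 to 0.47.

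**Sections 10.2, 3.1.4 and 8.2.** Keep the threshold. Record the probable/definite judgement for each related death, each related grade 4 hemolytic anemia event, and each related grade 3 or higher event in the DLT window. This adds one field for a small set of events and leaves the rates of suspension and de-escalation unchanged.

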## **10.3 POPULATIONS FOR ANALYSES**

### **10.3.1 Evaluable for Toxicity**

All patients who have received at least one dose of any of the study drugs will be evaluable for toxicity.

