## 1 INTRODUCTION

### 1.1 STUDY OBJECTIVES

#### 1.1.1 Primary Objective

To determine the safety of the triplet combination of magrolimab, venetoclax, and obinutuzumab in relapsed and refractory indolent B-cell malignancies

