### 3.1.2 Dose-Expansion Phase

Once safety is confirmed, expansion cohorts (Cohorts 3 and 4 and Arms 3 and 4) will be enrolled to collect additional safety information as well as disease response (Figure 5). During the dose expansion portion of the study, all patients will receive magrolimab with obinutuzumab for 2 cycles during the “window” period (i.e., Cycle -2 and Cycle -1) designed to assess for early clinical activity and correlates of response to magrolimab and obinutuzumab. The purpose of the window is to study the molecular and immunologic correlates of response to magrolimab-based therapy. It is not intended to provide complete information regarding the clinical activity of this doublet.

[figure not shown]
After completing the window, venetoclax will be added with the dose determined from the dose-finding cohorts as described above. Patients must fulfill the clinical and laboratory criteria mentioned in Table 9 below prior to addition of venetoclax. Patients with unequivocal PD during the treatment window who are tolerating therapy will be allowed to be moved immediately to the next phase (i.e., addition of venetoclax). After completion of Cycle 1, all patients will be treated with an additional five (5), 4-week cycles of triplet combination therapy (magrolimab and obinutuzumab and venetoclax). Final duration of therapy will be based on response to the first 6 cycles of triplet combination therapy. FL, MZL and MCL patients who achieve a CR and CLL patients who achieve a CR with undetectable peripheral blood MRD by flow cytometry after 6 cycles of triplet therapy will stop treatment but remain potentially eligible for an additional 6 cycles upon disease relapse provided that they still meet re-treatment criteria and the duration of CR is  $\geq$  6 months. Disease relapse is defined by conventional criteria for clinical relapse that is associated with radiographic progression. Additionally, for CLL patients, positive flow cytometry during follow-up will be considered relapsed for re-treatment. Reappearance of ctDNA is not considered disease relapse on this protocol. Patients who achieve a PR after 6 cycles of triplet combination therapy will be eligible to receive an additional 6 cycles and then will stop treatment.

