### **10.2 SAMPLE SIZE DETERMINATION AND STATISTICAL PLAN**

The primary endpoint of this trial is to determine the safety and tolerability of the combination of magrolimab and obinutuzumab with venetoclax. We will be assessing this endpoint by using a venetoclax dose-finding scheme. During dose-finding, patients will receive magrolimab and obinutuzumab at fixed doses, and venetoclax will be administered at DL1. If required, dose de-escalation of venetoclax will be explored. Patients will be enrolled in two cohorts for this evaluation: follicular lymphoma (FL) in Cohort 1, marginal zone lymphoma (MZL), chronic lymphocytic leukemia (MCL), and mantle cell lymphoma (CLL) in the Cohort 2. Unless dose de-escalation is required, 6 total patients will be enrolled from Cohort 1 into Arm 1, and 6 total patients will be enrolled from Cohorts 2 into Arm 2. Both Cohorts 1 and 2 will include a single dose de-escalation DL(-1) if needed. A maximum of 6 treated patients will be needed to complete the dose de-escalation scheme (if required) for Cohort 1, Arm 1, and a maximum of 6 treated patients will

be needed to complete the dose de-escalation scheme (if required) for Cohort 2, Arm 2 (total 24 patients).

At the MTD of venetoclax, dose expansion cohorts will enroll patients to assess the secondary clinical response outcomes in a preliminary fashion. The dose expansion cohorts (Cohorts 3, 4, 5 and 6), based on the results of dose-escalation in Cohorts 1 and 2, will open to accrue up to 18 additional FL patients, 6 additional MZL patients, 12 additional MCL patients and 6 additional CLL patients. These numbers were chosen based on the expected number of patients which could be accrued in two years after completion of the dose-finding phase. A total of 42 treated patients will be required to complete the dose expansion phase of the study.

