### **10.4.2 Analysis of the Primary Endpoints**

The type, number and frequency of DLTs to triplet combination therapy will be reported and described.

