### **10.4.4 Safety Analyses**

The type, grade and frequency of toxicities will be reported. DLTs, MTD of venetoclax in combination with magrolimab and obinutuzumab; and SAEs will be reported as well.

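### The supporting safety tables for the expansion cohorts do not separate the doublet window from the triplet period or define a venetoclax-exposed set; the primary DLT analysis is not affected

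*Combined protocol and SAP*

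**What the plan says.** The primary objective (1.1.1) is "To determine the safety of the triplet combination of magrolimab, venetoclax, and obinutuzumab in relapsed and refractory indolent B-cell malignancies". For toxicity, section 10.3 lists a single population, in 10.3.1: "All patients who have received at least one dose of any of the study drugs will be evaluable for toxicity". It contains no set defined by venetoclax exposure.

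On analysis, 10.4.1 promises a toxicity profile of the combination, and 10.4.4 says "The type, grade and frequency of toxicities will be reported". Neither divides adverse events by treatment period.

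Expansion patients receive two 28-day cycles of magrolimab and obinutuzumab before venetoclax (3.1.2, Table 12). Section 3.1.2 adds: "Patients must fulfill the clinical and laboratory criteria mentioned in Table 9 below prior to addition of venetoclax". It also gives these cohorts the job of collecting further safety information. Dose-finding patients have no window and start venetoclax on Cycle 1 Day 1 (Table 11). Section 10.2 allows the two groups to be combined: "Patients enrolled in dose-finding cohorts who are treated at the same dose-level as the expansion cohorts may be analyzed together with the dose-expansion cohorts".

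The primary endpoint is handled separately. Section 10.2 says "We will be assessing this endpoint by using a venetoclax dose-finding scheme", and 10.4.2 says "The type, number and frequency of DLTs to triplet combination therapy will be reported and described". Section 3.1.4 places that assessment: "Dose limiting toxicities (DLTs) will be assessed during the venetoclax dose-finding for Arms 1 and 2 as follows". Section 3.1.1 has its own evaluability rule: patients who withdraw before completing DLT assessment, for reasons other than a DLT, are not evaluable and are replaced. Section 10.4.3 lists DLTs on the doublet during the window as a separate secondary item.

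**The concern.** The trial's question is how safe three drugs are together. For most of the planned patients, the first eight weeks involve only two of them. An unsplit table over everyone dosed has three effects.

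- Toxicity arising on the doublet is shown as toxicity of the combination. This is predictable from the protocol. Section 3.3.5 places obinutuzumab infusion reactions mainly in the first 1000 mg, and 3.4.2.1 places the magrolimab hemoglobin nadir in most patients within the first two weeks. In expansion, both fall in Cycle -2.
- Toxicity arising once venetoclax is added is divided by a denominator that includes patients who never took it.
- Patients who reach venetoclax have come through the window and the Table 9 criteria. Mixing them with dose-finding patients, who met all three drugs in Cycle 1, hides that selection.

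DLTs cover only the first 28 or 35 days, in six patients per dose level. The triplet lasts 6 to 12 cycles. What the trial reports about triplet safety after Cycle 1, and in expansion at all, rests on these supporting tables.

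**Working it through.** **1. The plan's own count.** Dose-finding: 2 cohorts × 2 dose levels × 6 = 24. Expansion: 18 + 6 + 12 + 6 = 42. Total: 24 + 42 = 66, which matches section 10.2. Expansion is 42/66 = 64% of planned patients.

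**2. Share of time on the doublet**, on schedule through triplet Cycle 6 (Tables 11 and 12). FL: 56/(56 + 6 × 28) = 56/224 = 25.0%. MZL, MCL and CLL: 56/(56 + 35 + 5 × 28) = 56/231 = 24.2%.

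**3. Who can miss venetoclax.** In the window, delays beyond two weeks are not permitted, and a patient for whom restarting is then judged unsafe comes off treatment (3.3). Grade 4 non-hematologic toxicity (Table 17), recurrent grade 3 infusion reactions and grade 4 infusion reactions (3.3.4.3, Table 18) also end treatment. Withdrawal and unmet Table 9 criteria are further routes. Progression is not one: window progressors move on to the triplet (3.1.2, 3.10.1). Losses would therefore be mainly for toxicity, withdrawal or unmet criteria.

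**4. Dilution.** The documents give no share, so assume k = 0 to 8 of 42 never start venetoclax (about 0 to 20%), with a true triplet-period rate of 30% (also assumed). The rate over all 42 is 0.30 × (42 − k)/42.

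**5. Window events added.** Assume a proportion q of all 42 has the event in the window, independently of the triplet period. The any-time rate is [42q + (1 − q) × 0.30 × (42 − k)]/42.

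| k | On venetoclax | Step 4 | Step 5, q = 5% | Step 5, q = 10% | Step 5, q = 20% |
|---|---|---|---|---|---|
| 0 | 42 | 30.0% | 33.5% | 37.0% | 44.0% |
| 2 | 40 | 28.6% | 32.1% | 35.7% | 42.9% |
| 4 | 38 | 27.1% | 30.8% | 34.4% | 41.7% |
| 6 | 36 | 25.7% | 29.4% | 33.1% | 40.6% |
| 8 | 34 | 24.3% | 28.1% | 31.9% | 39.4% |

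The net error can go either way. It depends on how much of the event type arises in the window and on how many patients stop there.

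**6. Pooling under 10.2.** If both dose-finding cohorts stay at dose level 1, 12 patients join the 42. With k = 8, the diluted rate is (0.30 × 12 + 0.30 × 34)/54 = 13.8/54 = 25.6%. Pooling softens the dilution but does not remove it.

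**7. Effect on the primary analysis.** None of the up to 24 patients assessed for DLTs has a window, and venetoclax is scheduled from their first day. The DLT tables for Arms 1 and 2 do not change.

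**The case against.** A reader might infer that the primary objective itself is measured over window patients and window events. The documents do not support that. The primary endpoint is assessed through dose-finding and analyzed as DLTs in arms without a window, under their own evaluability rule. So 10.3.1 is the only toxicity population in 10.3, but not the only evaluability rule in the plan.

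A reader might also infer that nothing separates window toxicity, or that every patient who misses a Table 9 criterion is lost. Section 10.4.3 does report window DLTs separately. It covers DLTs only, however, and sits awkwardly with 3.1.4, which assesses DLTs in Arms 1 and 2, and with 3.1.5, which says DLT rules apply to all arms. On Table 9, section 3.1.2 requires the criteria before venetoclax but does not say that one miss removes a patient. Transfusions (Table 9) and growth factors (3.3.2) are permitted.

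Other objections carry weight. An any-dose safety population is conventional and rightly keeps patients who stop early for toxicity. Section 10.4.4 is descriptive, with no threshold or test. Pooling is optional. The illustrated shifts are small against the precision available: exact 95% intervals are 16 to 45% for 12/42 and 20 to 54% for 12/34. The protocol's infusion-reaction rates (45% in Table 6, 74% in the 1000 mg column of Table 5) come from different populations and regimens, so they do not size the effect here.

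These points limit the finding to the supporting tables. They do not supply the missing split: onset dates are recorded (8.2), but no analysis is specified that uses them.

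**Conclusion.** The point holds for the supporting safety analyses only. As specified, the expansion tables, and any pooled table under 10.2, would mix 56 days of doublet events and any patients never given venetoclax with triplet toxicity, for up to 42 of 66 patients.

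The size cannot be fixed from the documents. On the assumptions shown, a 30% triplet-period rate reads as low as 24.3% from dilution alone, or as high as 44.0% with 20% window-onset events and no losses. No dose decision in dose-finding and no primary result depends on this. It is an inexpensive improvement worth making before the tables are programmed.

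**What to change.** Keep 10.3.1 for overall safety and make these additions:

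- In 10.3, add a triplet safety set: patients with at least one venetoclax dose, counting adverse events with onset on or after the first venetoclax dose. Use it for expansion and pooled triplet toxicity tables.
- In 10.4.4, tabulate window adverse events separately, over all patients who started Cycle -2.
- Report how many expansion patients did not start venetoclax, and why.
- Show Cohorts 1–2 (no window) beside Cohorts 3–6 (after the window) before any pooling under 10.2.

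It would also help to list the DLT-evaluable set of 3.1.1 in 10.3, so that the primary analysis has a named population.

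Adverse event onset dates are already collected (8.2), and no treatment or visit changes. The cost is statistical wording, one extra set of adverse event tables, slightly smaller denominators and correspondingly wider intervals.
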